**Protocol Amendment 2 Rationale**

Amendment number:	Amendment 2, substantial
Rationale/background for changes:	

• A tertiary objective was added to allow potential exploratory evaluation of immune responses induced by the study vaccine(s) against a panel of strains of Neisseria species in a subset of subjects.

• Protocol Clarification Letter 1 was incorporated, which removed reference to a pregnancy electronic case report form.

• The window for Subject Diary reminder calls was clarified.

• Other minor changes were made to correct typos, and improve clarity and alignment within the document.

	

**SYNOPSIS**

Study title	A Phase II, Randomized, Open-label, Multicenter Study to Assess the Immunogenicity and Safety of GSK Meningococcal MenABCWY Vaccine, and of GSK Meningococcal Group B and MenACWY Conjugate Vaccines Administered Concomitantly in the Same Arm or in 2 Different Arms, or Alone in Healthy Subjects 10 to 25 Years of Age
EudraCT number	2017-005128-12
Study protocol number	208205 MENABCWY-016 (V102_19) Final: 09 February 2018 Amendment 1 Final: 15 May 2018 Amendment 2 Final: 29 August 2018
Investigational product (primary study vaccine and number)	GlaxoSmithKline (GSK) Biologicals' meningococcal MenABCWY vaccine (GSK3536819A)
Phase	II
Rationale for the study	In previous clinical studies of MenABCWY versus rMenB+OMV NZ, immune responses against serogroup B antigens were lower than immune responses assessed when rMenB+OMV NZ was administered alone. One possible reason that has been theorized is biological immune interference, possibly due to immunological stress to the lymph nodes in the arm where the combination vaccine is administered. The purpose of the current study is to evaluate whether there is immune interference when MenABCWY is administered to healthy adolescents and adults.
Risk/Benefit assessment	No significant safety signals have been identified for MenABCWY. Cumulative safety data have not identified new important safety risks. The balance of anticipated benefits and apparent risks associated with MenABCWY continues to be acceptable following the ongoing systematic review of safety data.
	Taking into account the measures taken to minimize risk to subjects participating in this study, the potential or identified risks identified in association with rMenB+OMV NZ, MenACWY, and MenABCWY are justified by the potential benefits (prevention/treatment) that may be afforded to subjects.

Used medicinal products	Primary study vaccine 

• GSK Biologicals' meningococcal MenABCWY vaccine (GSK3536819A)

 Other study vaccines 

• GSK Biologicals' meningococcal rMenB+OMV NZ vaccine (Bexsero; GSK3536829A)

• GSK Biologicals' meningococcal MenACWY vaccine (Menveo; GSK3536820A)

Number of subjects	Target enrollment will be approximately 500 subjects (approximately 100 subjects per group). The sample size is for exploratory statistical analysis purposes only.
Purpose of this clinical study	This Phase II, randomized, open-label clinical study is designed to evaluate the potential immune interference when MenABCWY is administered to healthy subjects as 2 injections, 2 months apart.
Indication	Primary immunization against Neisseria meningitidis serogroups A, B, C, W-135, and Y.
Objectives	Primary 

• To assess the immune response to 2 doses of MenABCWY, rMenB+OMV NZ, or rMenB+OMV NZ and MenACWY administered concomitantly in the same arm or in 2 different arms, and to a single dose of MenACWY at 1 month after the last vaccination.

 Secondary Immunogenicity Objective 

• To assess the immune response to 2 doses of MenABCWY, rMenB+OMV NZ, or rMenB+OMV NZ and MenACWY administered concomitantly in the same arm or in 2 different arms at 1 month after the first vaccination.

 Safety Objective 

• To assess the safety and tolerability of 2 doses of MenABCWY, rMenB+OMV NZ, or rMenB+OMV NZ and MenACWY administered concomitantly in the same arm or in 2 different arms, and to a single dose of MenACWY.

**Tertiary**

- *To further characterize the immune response induced by the study vaccine(s) against an additional panel of strains of *Neisseria* species in a subset of subjects.*

*Note: This tertiary objective is exploratory and suitable assays may or may not be developed. The tertiary objective will be assessed in a subset of subjects using remaining serum after the primary and secondary analyses have been completed; no additional blood samples will be collected from subjects. Any outcome of exploratory testing that would be of scientific/medical relevance will be reported in an annex/addendum to the final study report.*

*(Amended 29 Aug 2018)*

**Method of evaluation****Primary**

- Immune responses against *N. meningitidis* serogroup B\* test strains and *N. meningitidis* serogroups A, C, W-135, and Y, as measured by a serum bactericidal assay using human complement (hSBA), 1 month after the last vaccination in all study groups
  - hSBA geometric mean titers (GMTs) against each of the *N. meningitidis* serogroup B test strains and against *N. meningitidis* serogroups A, C, W-135, and Y
  - hSBA GMTs against all of *N. meningitidis* serogroup B test strains (pooled)
  - Percentage of subjects with hSBA titers  $\geq$  the lower limit of quantitation (LLOQ) against each *N. meningitidis* serogroup B test strains and against *N. meningitidis* serogroups A, C, W-135, and Y
  - Percentage of subjects with a 4-fold increase in hSBA titers against *N. meningitidis* serogroups B test strains and against *N. meningitidis* serogroups A, C, W-135, and Y
  - hSBA geometric mean ratios (GMRs) against each of the *N. meningitidis* serogroup B test strains and against *N. meningitidis* serogroups A, C, W-135, and Y at 1 month after the last vaccination against baseline (Day 1)

\*Serogroup B strains that will be tested are M14459 (factor H binding protein; fHbp), 96217 (Neisserial adhesin A; NadA), NZ98/254 (PorA), and M07-0241084 (Neisseria heparin

binding antigen; NHBA) and will be pooled to estimate the effect of immune interference due to stress to lymph nodes.

Note: A 4-fold rise is defined as: a) for individuals whose pre-vaccination titers are < the limit of detection (LOD), the post-vaccination titers must be  $\geq$ 4-fold the LOD or  $\geq$  the LLOQ, whichever is greater; b) for individuals whose pre-vaccination titers are  $\geq$  the LOD and < the LLOQ, the post-vaccination titers must be at least 4 times the LLOQ; and c) for individuals whose pre-vaccination titers are  $\geq$  the LLOQ, the post-vaccination titers must be at least 4 times the pre-vaccination titer.

### **Secondary**

#### Immunogenicity Endpoints

- Immune responses against *N. meningitidis* serogroup B test strains and *N. meningitidis* serogroups A, C, W-135, and Y, as measured by hSBA, 1 month after the first vaccination in all groups (except for subjects in the MenACWY group)

The statistical analyses and comparisons for the secondary immunogenicity endpoints will be the same as described for the primary endpoint.

#### Safety Endpoints

- Solicited local and systemic adverse events (AEs) in all study groups
  - Occurrence of solicited local and systemic AEs during the 7 days (including the day of vaccination) after each vaccination (Day 1 to Day 7 and Day 61 to Day 67 [Day 1 to Day 7 only for subjects in the MenACWY group])
- Unsolicited AEs in all study groups
  - Occurrence of unsolicited AEs during the 30 days (including the day of vaccination) after each vaccination (Day 1 to Day 31 and Day 61 to Day 91 [Day 1 to Day 31 only for subjects in the MenACWY group])
- Serious AEs (SAEs), medically attended AEs, AEs leading to withdrawal, and AEs of special interest, in all study groups from informed consent signature to Visit 4 (Day 91)

Note: Arthritis is the only AE of special interest in this study.

***Tertiary***

***Endpoints related to the tertiary objective will be described in a separate statistical analysis plan. (Amended 29 Aug 2018)***

**Study population****Inclusion criteria**

All subjects must satisfy ALL the following criteria at study entry:

1. Subjects and/or subjects' parent(s)/Legally Acceptable Representative(s) (LARs) who, in the opinion of the investigator, can and will comply, with the requirements of the protocol (e.g. completion of the paper diary [pDiary], return for follow-up visits, availability for all visits scheduled in the study).
2. Written informed consent obtained from the subject and/or from the parent(s)/LAR(s) of the subject prior to performing any study specific procedure.
3. Written informed assent obtained from subjects below the legal age of consent prior to performing any study specific procedure.
4. A male or female between, and including, 10 to 25 years of age at the time of the first vaccination.
5. Healthy subjects as established by medical history and clinical examination before entering into the study.
6. Female subjects of non-childbearing potential may be enrolled in the study.
  - Non-childbearing potential is defined as pre-menarche, current bilateral tubal ligation or occlusion, hysterectomy, or bilateral ovariectomy.
7. Female subjects of childbearing potential may be enrolled in the study, if the subject:
  - has practiced highly effective contraception for 30 days prior to vaccination, and
  - has a negative pregnancy test on the day of vaccination, and
  - has agreed to continue highly effective contraception during the entire treatment period and for 2 months after completion of the vaccination series.

**Exclusion criteria**

If ANY exclusion criterion applies, the subject must not be included in the study:

1. Female planning to become pregnant or planning to discontinue contraceptive precautions.
2. Pregnant or lactating female.
3. Child in care.

Each subject must not have:

4. Current or previous, confirmed or suspected disease caused by *N. meningitidis*.
5. Known contact to an individual with any laboratory-confirmed *N. meningitidis* infection within 60 days prior to enrollment.
6. Previous vaccination against *N. meningitidis* at any time prior to informed consent.
7. Progressive, unstable or uncontrolled clinical conditions.
8. Hypersensitivity, including allergy, to any component of vaccines, medicinal products or medical equipment whose use is foreseen in this study.
9. Clinical conditions representing a contraindication to intramuscular (IM) vaccination and blood draws.
10. Abnormal function of the immune system resulting from:
  - Clinical conditions.
  - Systemic administration of corticosteroids (oral/intravenous/IM) for more than 14 consecutive days within 90 days prior to informed consent.
  - Administration of antineoplastic and immune-modulating agents or radiotherapy within 90 days prior to informed consent.
11. Received immunoglobulins or any blood products within 180 days prior to informed consent.
12. Received an investigational or non-registered medicinal product within 30 days prior to informed consent.
13. Any other clinical condition that, in the opinion of the investigator, might interfere with the results of the study or pose additional risk to the subject due to participation in the study.
14. Concurrently participating in another clinical study, at any time during the study period, in which the subject has been

or will be exposed to an investigational or a non-investigational vaccine/product (pharmaceutical product or device).

15. Acute or chronic, clinically significant pulmonary, cardiovascular, hepatic, or renal functional abnormality, as determined by physical examination.
16. Any confirmed or suspected immunosuppressive or immunodeficient condition, based on medical history and physical examination (no laboratory testing required).
17. Are obese at screening (e.g. with a body mass index [BMI]  $\geq 30 \text{ kg/m}^2$ , where BMI reflects obesity and not high muscle mass).
18. Family history of congenital or hereditary immunodeficiency.
19. History of neuroinflammatory or autoimmune condition.
20. History of significant neurological disorder or seizure (history of febrile convulsion should not lead to exclusion).
21. Serious chronic illness.
22. History of chronic alcohol consumption and/or drug abuse (including current consumption/abuse).
23. Any study personnel as an immediate family or household member.
24. Administration of a vaccine not foreseen by the study protocol in the period starting 14 days (for inactivated vaccines), 28 days (for live vaccines), or 7 days (for influenza vaccines) before each dose and ending 14 days (for inactivated vaccines), 28 days (for live vaccines), or 7 days (for influenza vaccines) after each dose of study vaccine(s) administration.
25. Thrombocytopenia, bleeding disorders, or be receiving anticoagulant therapy.

**Criteria for withdrawal from the study**

From an analysis perspective, a “withdrawal” from the study refers to when a subject does not come back for the concluding visit foreseen in the protocol. A subject is considered “withdrawn” from the study when no study procedure has occurred, no follow-up has been performed, and no further information has been collected for this subject from the date of withdrawal/last contact. Information relative to the withdrawal will be documented in the electronic case report form (eCRF). The investigator will document whether the decision to withdraw a subject from the study was made by the subject

himself/herself, by the subject's parent(s)/LAR(s), or by the investigator.

A "withdrawal" from the study vaccine(s) refers to when a subject any subject who does not receive the complete treatment, i.e. when no further planned dose is administered from the date of withdrawal. A subject withdrawn from the study vaccine(s) may not necessarily be withdrawn from the study as further study procedures or follow-up may be performed (safety or immunogenicity) if planned in the study protocol. Information relative to premature discontinuation of the study vaccine(s) will be documented in the eCRF.

Reasons was responsible for withdrawal:

- Serious AE
- Unsolicited non-serious AE
- Solicited AE
- Protocol violation (specify)
- Consent withdrawal, not due to an AE
- Moved from the study area
- Lost to follow-up
- Other (specify)

**Treatment, Dose level(s)** See Dosage and Administration Table.

**Synopsis Table 1 Dosage and administration**

Type of contact and time point	Study group	Treatment name	Volume to be administered	Route 	Site		
					Location	Directionality 	Laterality 
Visit 1 (Day 1)	MenABCWY	MenABCW Y 	0.5 mL	IM	Deltoid	Upper or lower	Non-dominant
	rMenBOMV+A CWY_S 	rMenB+O MV NZ	0.5 mL		Upper Deltoid (approximately 2.5 cm above MenACWY injection)	Upper	Non-dominant
		MenACWY 6	0.5 mL		Lower Deltoid (approximately 2.5 cm below rMenB+OMV NZ injection)	Lower	Non-dominant
	rMenBOMV+A CWY_D 	rMenB+O MV NZ	0.5 mL		Deltoid	Upper or lower	Non-dominant
		MenACWY 6	0.5 mL		Deltoid	Upper or lower	Dominant
	rMenBOMV	rMenB+O MV NZ	0.5 mL		Deltoid	Upper or lower	Non-dominant
	MenACWY	MenACWY 6	0.5 mL		Deltoid	Upper or lower	Non-dominant
Visit 3 (Day 61)	MenABCWY	MenABCW Y 	0.5 mL	IM	Deltoid	Upper or lower	Non-dominant
	rMenBOMV+A CWY_S 	rMenB+O MV NZ	0.5 mL		Upper Deltoid (approximately 2.5 cm above MenACWY injection)	Upper	Non-dominant
		MenACWY 6	0.5 mL		Lower Deltoid (approximately 2.5 cm below rMenB+OMV NZ injection)	Lower	Non-dominant
		rMenBOMV+A CWY_D 	rMenB+O MV NZ		Deltoid	Upper or lower	Non-dominant
			MenACWY 6		Deltoid	Upper or lower	Dominant
	rMenBOMV	rMenB+O MV NZ	0.5 mL		Deltoid	Upper or lower	Non-dominant

Intramuscular (IM)Directionality is a qualifier for further detailing the location of the vaccine(s) administration (e.g. Upper, Lower)The non-dominant arm is the preferred arm of injection. In case it is not possible to administer the vaccine(s) in the non-dominant arm, an injection in the dominant arm may be performed.MenABCWY is to be reconstituted as a 0.5 mL solution between MenACWY lyo (lyophilized component) and rMenB+OMV NZ (liquid component) by trained staff.S refers to administration in the same arm (approximately 2.5 cm apart).MenACWY is to be reconstituted as a 0.5 mL solution between Men A lyo (lyophilized component) and Men CWY liquid (liquid component) by trained staff.D refers to administration in 2 different arms.

Route of administration	IM
Excluded concomitant medications	
The use of the following concomitant medications/products/vaccines will not require withdrawal of the subject from the study but may determine a subject's evaluability in the per-protocol analysis.
 

• Any investigational or non-registered product (drug or vaccine) other than the study vaccine(s) used during the study period.

• Immunosuppressants or other immune-modifying drugs administered chronically (i.e. more than 14 consecutive days in total) during the study period. Inhaled and topical steroids are allowed.

• Long-acting immune-modifying drugs administered at any time during the study period (e.g. infliximab).

• A vaccine not foreseen by the study protocol administered during the period of 14 days (for inactivated vaccines), 28 days (for live vaccines), or 7 days (for influenza vaccines) before or after administration of the study vaccine(s) at Visit 1 and Visit 3.

• Drug and/or alcohol abuse that, in the opinion of the investigator, will interfere with the results of the study or pose additional risk to the subject.

Overview of the study design	
This Phase II, randomized, open-label clinical study is designed to evaluate the potential immune interference when MenABCWY is administered to healthy subjects as 2 injections, 2 months apart. To accomplish this aim, immune responses to MenABCWY will be assessed and compared with responses to MenACWY (Menveo) and rMenB+OMV (Bexsero) when administered concomitantly (in the same arm or in 2 different arms) or either vaccine alone. Immune responses will be measured by hSBA using a standard panel consisting of N. meningitidis serogroup A, C, W-135, and Y and serogroup B test strains directed against each of the major corresponding meningococcal antigens included in the vaccines (Men B test strains for rMenB+OMV NZ and Men A, C, W-135, and Y test strains for MenACWY). Concomitant administration of MenACWY and rMenB+OMV NZ vaccines in the same arm (approximately 2.5 cm apart) or in 2 different arms will allow evaluation of a potential immune interference due to immunological stress to lymph nodes in the arm where the combination vaccine is administered.

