**Study design**

- Experimental design: Phase II, open-label, randomized, controlled, multi-centric, study with 5 parallel study groups
- Duration of the study: Up to 91 days (4 visits, 30 days apart)
  - Epoch 001: Starting at Visit 1 (Day 1) and ending at Visit 4 (Day 91)
- Primary Completion Date: Visit 4 (Day 91)
- End of Study: Date of the last testing results released for the samples collected at Visit 4 (Day 91), to be achieved no later than 8 months after the Last Subject Last Visit
- Study groups:

Approximately 500 subjects will be randomly assigned at a 1:1:1:1:1 ratio to receive one of the following:

  - MenABCWY: Approximately 100 subjects (50 subjects aged 10 to 17 years and 50 subjects aged 18 to 25 years) will receive 1 IM dose of MenABCWY twice, 2 months apart.
  - rMenBOMV+ACWY\_S: Approximately 100 subjects (50 subjects aged 10 to 17 years and 50 subjects aged 18 to 25 years) will concomitantly receive 1 IM dose of rMenB+OMV NZ and 1 IM dose of MenACWY in the same arm (approximately 2.5 cm apart) twice, 2 months apart.
  - rMenBOMV+ACWY\_D: Approximately 100 subjects (50 subjects aged 10 to 17 years and 50 subjects aged 18 to 25 years) will concomitantly receive 1 IM dose of rMenB+OMV NZ and 1 IM dose of MenACWY in 2 different arms twice, 2 months apart.
  - rMenBOMV: Approximately 100 subjects (50 subjects aged 10 to 17 years and 50 subjects aged 18 to 25 years) will receive 1 IM dose of rMenB+OMV NZ twice, 2 months apart.
  - MenACWY: Approximately 100 subjects (50 subjects aged 10 to 17 years and 50 subjects aged 18 to 25 years) will receive 1 IM dose of MenACWY once.

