### **1.2.2. Rationale for the study design**

This Phase II, randomized, open-label clinical study is designed to evaluate the potential immune interference when MenABCWY is administered to healthy subjects as 2 injections, 2 months apart. To accomplish this aim, immune responses to MenABCWY will be assessed and compared with responses to MenACWY and rMenB+OMV when administered concomitantly (in the same arm or in 2 different arms) or either vaccine alone. Immune responses will be measured by a serum bactericidal assay using human complement (hSBA) using a standard panel consisting of *N. meningitidis* serogroup A, C, W-135, and Y and serogroup B test strains directed against each of the major corresponding meningococcal antigens included in the vaccines (Men B test strains for rMenB+OMV NZ and Men A, C, W-135, and Y test strains for MenACWY). Concomitant administration of MenACWY and rMenB+OMV NZ vaccines in the same arm (approximately 2.5 cm apart) or in 2 different arms will allow evaluation of a potential immune interference due to immunological stress to lymph nodes in the arm where the combination vaccine is administered.

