#### Analysis of hSBA GMT

An analysis of covariance (ANCOVA) model will be used to analyze post-vaccination log-transformed titers of hSBA for both the primary and secondary objectives (i.e. the hSBA at 1 month after the last vaccination and the hSBA at 1 month after the first vaccination, respectively). The ANCOVA model will be fitted to each serogroup/strain individually, and in addition the serogroup B strains will be grouped together to perform a pooled analysis. The GMTs obtained through the ANCOVA model will be called “adjusted” and the “unadjusted” GMTs will be obtained through descriptive statistics. Unadjusted and adjusted GMTs and associated 2-sided 80% CIs will be computed for each study group and for each strain at each visit. The fixed-effect model will include the age strata, treatment, serogroup, and center as fixed effects. The pre-vaccination log-transformed titer with centering at zero will be included as a continuous covariate. An interaction between serogroup and pre-vaccination log-transformed titer centered at zero will be included in the model. For each study group, adjusted GMTs and their 80% CIs will be obtained by exponentiating (base 10) the least squares means and the lower and upper limits of the 80% CIs of the log-transformed titers (base 10).

The following contrasts will be computed to investigate possible effects on the immune response based on strains common to each treatment group:

- a. rMenBOMV+ACWY\_S versus rMenBOMV+ACWY\_D (test for immune interference, due to immunological stress to lymph node)
- b. MenABCWY versus rMenBOMV+ACWY\_S (test for other unknown immunological interference)
- c. rMenBOMV+ACWY\_S versus rMenBOMV
- d. rMenBOMV+ACWY\_S versus MenACWY
- e. rMenBOMV+ACWY\_D versus rMenBOMV
- f. rMenBOMV+ACWY\_D versus MenACWY
- g. MenABCWY versus rMenBOMV
- h. MenABCWY versus MenACWY

In addition, the distribution of antibody titers for each strain will be displayed using reverse cumulative distribution curves.

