### ANCOVA2

- The fixed-effect model will include age strata, study group, strain\*\* and center as fixed effects. The pre-vaccination (Baseline) log-transformed titer with centering at zero will be included as a continuous covariate. An interaction between strain\* and pre-vaccination log-transformed titer centered at zero will be included in the model.
- The model will be fitted to the serogroup B test strain data only.

\*\* a categorical variable will be used to indicate if the dependent variable (response) is for serogroup B test strain M14459, 96217, NZ98/254 or M07-0241084.

For each study group, adjusted GMTs, SEs and 80% CI for GMT will be obtained by taking the anti-logarithm of the least squares means, the SE and the lower and upper limits of the 80% CIs of the log-transformed titers. The pre-vaccination log-transformed titer will be zero centered as follows: *log-transformed titer for each subject at Baseline – mean(log-transformed titer for all subjects at Baseline)* i.e. centering will occur after the titer results have been log transformed.

The contrasts in Table 6 will be computed at AVISIT 4 based on PPS3 to investigate possible effects on the immune response based on strains common to each study group.

No adjustment will be made for multiple comparisons.

rMenBOMV+ACWY\_S will be declared statistically inferior if the 2-sided 80% CIs of the ratio of the GMT with rMenBOMV+ACWY\_D as control is lower than 1 at 1 month after last vaccination. The lymph-node effect would therefore be the most probable cause for the decrease observed.

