**Table 6 Contrasts for GMT from ANCOVA Models - Primary**

Contrast	Serogroup and Strains	Model
rMenBOMV+ACWY_S versus rMenBOMV+ACWY_D (test for immune interference, due to immunological stress to lymph node)	A, C, W-135, Y Individual B strains Pooled B strains	ANCOVA1
MenABCWY versus rMenBOMV+ACWY_S (test for other unknown immunological interference)		ANCOVA1
rMenBOMV+ACWY_S versus rMenBOMV		ANCOVA1
rMenBOMV+ACWY_S versus MenACWY	A, C, W-135, Y	ANCOVA1
rMenBOMV+ACWY_D versus rMenBOMV	Individual B strains	ANCOVA1
rMenBOMV+ACWY_D versus MenACWY	A, C, W-135, Y	ANCOVA1
MenABCWY versus rMenBOMV	Individual B strains	ANCOVA1
MenABCWY versus MenACWY	A, C, W-135, Y	ANCOVA1

The following outputs will be produced:

- Unadjusted and adjusted summary statistics (n, GMT, GSD, 80% CI for GMT, minimum, maximum, ANCOVA results: GMT, SE, 80% CI for GMT) at Baseline and AVISIT 4, based on PPS3.
- Contrasts from Table 6.

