## 8.2 Geometric Mean Ratios

### 8.2.1 Primary Endpoint

GMR will be summarized by study group at AVISIT 4 for each serogroup (A, C, W-135, Y) and the four individual serogroup B test strains. Missing titer results and results below the LOD will be handled as described in Section 4.3.

Unadjusted and adjusted summaries will be calculated and presented in the same output.

GMR will be calculated as the anti-logarithm of the mean of the change from baseline of log-transformed titer values at AVISIT 4 and Baseline i.e. anti-logarithm of  $\sum(\log_{10}(\text{titer}_{\text{AVISIT 4}}) - \log_{10}(\text{titer}_{\text{Baseline}}))/n$  where n is the number of subjects with non-missing titer results at Baseline and AVISIT 4.

Unadjusted summaries will include the number of subjects with non-missing titer results at AVISIT 4, GMR, GSD of the difference in log-transformed titer results at AVISIT 4 and Baseline, 80% CI for GMR, minimum and maximum.

GSD will be calculated as the anti-logarithm of the SD of the change from baseline of the log-transformed data. The 80% CI for GMR will be calculated as the anti-logarithm of the endpoints of the 80%CI for the mean GMR. The anti-logarithm is calculated as  $10^x$  where  $x$  is the statistic of interest calculated from the log-transformed data (e.g. mean, SD, 80% CI endpoints).

Adjusted summaries will be calculated using an ANCOVA model. The adjusted GMR, SE and 80% CI from the ANCOVA model will be presented. ANCOVA1 from Section 8.1.1 will be fitted to each serogroup/strain individually.

For each study group, adjusted GMRs, SEs and 80% CI for GMR will be obtained by taking the anti-logarithm of the least squares means, the SE and the lower and upper limits of the 80% CIs of the difference between log-transformed titers. The pre-vaccination log-transformed titer will be zero centered as follows: *log-transformed titer for each subject at Baseline – mean(log-transformed titer for all subjects at Baseline)* i.e. centering will occur after the titer results have been log transformed.

The contrasts in Table 6 will be computed (ANCOVA1 only) based on PPS3 to investigate possible effects on the immune response based on strains common to each study group.

No adjustment will be made for multiple comparisons.

The following results will be produced and presented in the same output containing the results from Section 8.1.1:

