### **8.3 Summary and Analysis of Percentage of Subjects With Titers Above LLOQ**

#### **8.3.1 Primary Endpoint**

This endpoint will be summarized for PPS3.

The percentage of subjects with titers above the LLOQ as well as the associated 2-sided 80% Clopper-Pearson CIs [Clopper, 1934] will be computed by study group at AVISIT 4.

In addition, differences in percentages of subjects with titers above the LLOQ and 2-sided 80% CIs between selected study groups will be calculated using the method of Miettinen and Nurminen [Miettinen, 1985]. The following differences will be calculated:

- rMenBOMV+ACWY\_S versus rMenBOMV+ACWY\_D (test for immune interference, due to immunological stress to lymph node)
- MenABCWY versus rMenBOMV+ACWY\_S (test for other unknown immunological interference)
- rMenBOMV+ACWY\_S versus rMenBOMV
- rMenBOMV+ACWY\_S versus MenACWY
- rMenBOMV+ACWY\_D versus rMenBOMV
- rMenBOMV+ACWY\_D versus MenACWY
- MenABCWY versus rMenBOMV
- MenABCWY versus MenACWY

No adjustments will be made for multiple comparisons.

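### The design text promises MenABCWY against separate-arm co-administration, but no planned analysis includes that contrast; the gap is mainly for serogroups A, C, W-135 and Y

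*Protocol*

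**What the plan says.** Below, M is MenABCWY, S is rMenBOMV+ACWY_S (same arm) and D is rMenBOMV+ACWY_D (different arms).

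- **Design text.** The Synopsis (Overview of the study design) and Protocol 1.2.2 both say that, to meet the study aim, M will be compared with the two licensed vaccines "when administered concomitantly (in the same arm or in 2 different arms) or either vaccine alone". Protocol 10.8 and SAP 8 add that a main objective is to estimate interference in the arm receiving the combination, relative to separate injections in two arms.
- **Protocol analysis.** Protocol 10.8 introduces items a to h with "The following contrasts will be computed to investigate possible effects on the immune response based on strains common to each treatment group". The eight pairs are S/D, M/S, S/rMenBOMV, S/MenACWY, D/rMenBOMV, D/MenACWY, M/rMenBOMV and M/MenACWY. Protocol 10.1 and 10.2 (items a to c) imply no further pair.
- **SAP analysis of titers.** SAP 3.2 repeats the Protocol lists. SAP 8.1.1 says "The contrasts in Table 6 will be computed at AVISIT 4 based on PPS3 to investigate possible effects on the immune response", and Table 6 holds the same eight pairs. Table 7 (1 month after dose 1) keeps the five pairs without MenACWY. For GMR, SAP 8.2.1 says "The contrasts in Table 6 will be computed (ANCOVA1 only) based on PPS3", and 8.2.2 uses Table 7.
- **SAP analysis of percentages.** After "The following differences will be calculated", SAP 8.3.1 lists the same eight pairs and 8.3.2 the same five. SAP 8.4 repeats 8.3 for the 4-fold rise.

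M/D is in none of these lists.

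**The concern.** The study asks whether giving MenABCWY causes immune interference. The plan splits that into a lymph-node part (S/D) and an unexplained remainder (M/S). The whole, on the log scale, is the sum of the two: M/D. It says how much response is lost by giving the combination in one arm instead of the same two vaccines in separate arms on the same schedule. The design text names that comparison, and the analysis lists then leave it out.

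For A, C, W-135 and Y, no other planned contrast fills the gap. S carries any same-arm effect itself. The MenACWY group "will receive 1 IM dose of MenACWY once", so after the last vaccination M/MenACWY mixes interference with the number of doses.

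**Working it through.** **Step 1. Which comparators M has.** Sources: Protocol 10.1, 10.2 and 10.8; SAP Tables 6 and 7, and 8.3. Some cells of Table 6 run together in the text I have, but its contrast names are readable and agree with the Protocol list and the intact Table 7.

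| Time point | Strains | Planned comparators for M | Any dose-matched and free of a same-arm effect? |
|---|---|---|---|
| 1 month after last vaccination | A, C, W-135, Y | S; MenACWY | No: S shares the arm; MenACWY is 1 dose against 2 |
| 1 month after last vaccination | B strains | S; rMenBOMV | Yes: rMenBOMV, 2 doses against 2 |
| 1 month after dose 1 | A, C, W-135, Y | S only | No |
| 1 month after dose 1 | B strains | S; rMenBOMV | Yes: rMenBOMV |

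At 1 month after dose 1 the MenACWY group would be dose-matched, but SAP 8.1.2 excludes it from the secondary analyses.

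**Step 2. The plan's own figure.** Inputs from Protocol 10.4: n = 100 per group, SD 0.435 (log10), difference -0.130, one-sided alpha 0.10.

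- SE = 0.435 × √(2/100) = 0.0615.
- Noncentrality = 0.130/0.0615 = 2.11, with 198 degrees of freedom.
- Power = 0.796, as stated. All 16 rows of Table 14 reproduce within 0.001.

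**Step 3. Why the two planned intervals do not give the third.** Let v be the variance of one group mean, with equal groups.

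- Point estimate: log(M/D) = log(M/S) + log(S/D). Within one ANCOVA1 fit this is exact.
- Var(M−S) = 2v, Var(S−D) = 2v, and Cov = −v because S enters both with opposite sign. The correlation is −v/2v = −0.5.
- Var(M−D) = 2v + 2v − 2v = 2v.

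Simulated ANCOVA1 layouts (500 subjects, 5 to 20 centers, both assumed) also gave a correlation of about −0.5.

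For illustration only: treating the two estimates as independent uses 4v, so the interval is √2 = 1.41 times too wide on the log scale, and a nominal 80% interval covers 2Φ(1.2816 × √2) − 1 = 93%. Nobody plans this method.

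**Step 4. What can be rebuilt from planned output.**

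- Percentages: counts and percentages are reported by group, so a Miettinen-Nurminen interval for M minus D can be computed directly.
- Unadjusted GMT and GMR: n, the mean and the GSD are reported by group, so a two-sample interval can be computed.
- Adjusted GMT: each group's estimate and SE are reported. The ratio is exact. Combining the SEs as √(SE₁² + SE₂²) ignores the covariance of the least squares means. In the simulated layouts the resulting interval was correct with equal center sizes and about 18% to 20% too wide with very uneven ones.

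**Step 5. Precision of the direct contrast (illustrative).** With SD 0.435, the 80% half-width is 1.286 × 0.0615 = 0.0791, a factor of 10^0.0791 = 1.20 either side. That SD is for the average of the four B strains. The documents give none for a single strain or for A, C, W-135 or Y. Assuming 0.5 to 0.7, the factor is 1.23 to 1.34.

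**The case against.** The strongest reply has four parts.

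- **The information is nearly all there.** Step 4 shows that only the exact adjusted interval is out of reach. This stands. A reader might infer that M/D would have no valid estimate at all, or that the trial would be left with an interval 1.41 times too wide. The documents do not support either, since group summaries for M and D are both planned outputs.
- **The motivating question is covered.** The rationale is a lower serogroup B response than with rMenB+OMV NZ alone. M/rMenBOMV is planned for each B strain at both time points. This stands, and confines the gap mainly to A, C, W-135 and Y, where the documents report no earlier loss.
- **D has another stated role.** The design text also says the same-arm and different-arm groups serve to evaluate the lymph-node effect. That is true, but it does not remove the earlier sentence naming D as a comparator for MenABCWY.
- **Nothing is decided on M/D.** Protocol 10.10 makes all analyses descriptive, and the only decision rule is S against D. This stands, so a power figure for M/D is not a property of the plan. The 0.74 ratio behind the power calculation also comes from MenABCWY against the MenB group in the earlier study, not from M/D.

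None of this explains why a comparison named in the design text is absent from every list.

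**Conclusion.** The mismatch is real: the design text names separate-arm co-administration as a comparator for MenABCWY, and no planned GMT, GMR or percentage comparison includes it. What is lost is a planned, reported, covariate-adjusted M/D contrast with its exact interval. It matters most for A, C, W-135 and Y. After the last vaccination D is the only two-dose comparator without a same-arm effect, and after dose 1 the only planned MenABCWY contrast is against S. For B strains the loss is small.

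The omission and the −0.5 correlation for equal groups follow from the documents and from algebra. The absolute interval factors rest on an SD for averaged B strains or on assumed SDs, and are illustrative only. This should be corrected, but it does not undermine the planned S/D test.

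**What to change.** Add MenABCWY versus rMenBOMV+ACWY_D, for A, C, W-135, Y and the individual B strains from ANCOVA1, to Protocol 10.1, 10.2 and 10.8 and to SAP 3.2 and Tables 6 and 7. SAP 8.2 then picks it up by reference. Add the same pair to the difference lists in SAP 8.3.1 and 8.3.2, and so to 8.4. Report it as the total effect, with S/D and MenABCWY/S as its two parts.

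The cost is one more estimate statement in models already fitted and one more row in existing tables, with no new data or subjects. The downside is one more exploratory contrast without multiplicity adjustment, as for all the others. If the sponsor does not want the contrast, the Synopsis overview and Protocol 1.2.2 should be reworded to match the analysis.
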